6.5.3. Benserazide Safety Population

All subjects who receive any amount of benserazide (as provided by the Sponsor) will be included in the Benserazide Safety Population. This population will be used for the analysis of the safety data collected after receiving benserazide (as provided by the Sponsor) and before receiving INP103 or placebo. This population will not be applicable to Cohort 4.

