6.5.4. Safety Population

All subjects who receive any amount of INP103 or placebo will be included in the Safety Population. The data will be analyzed according to the treatment received. All safety results will be generated on Safety Population.

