8. GENERAL CONSIDERATIONS FOR DATA ANALYSES

The listings, figures and summary tables for the disposition, safety, PK, and PDyn data will be the responsibility of the study Biostatistician at CNS.

The currently supported version of SAS software will be used to perform all data analyses, excluding the estimation of PK parameters, which will be undertaken with WinNonlin. The actual SAS and WinNonlin versions used will be presented in the Clinical Study Report (CSR).

All data in the database will be presented in the data listings. Unless otherwise stated, all listings will be sorted by cohort, randomized treatment group, subject number and assessment date/time.

Unless otherwise stated, continuous variables will be summarized using descriptive statistics including number of non-missing observations, mean, standard deviation (SD), median, minimum and maximum values.

Categorical variables will be summarized with frequency counts and percentages. The population size (N for sample size and n for available data) and the percentage (of available data) for each class of the variable will be presented. Percentages will be rounded to one decimal place, with the denominator being the number of subjects in the relevant population, unless otherwise stated.

Only data from nominal protocol scheduled visits will be included in the summary tables. Data from unscheduled visits will not be included in the summary tables but will be included in the figures and listings.

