11. SAFETY ANALYSES

All safety analyses will be conducted on the Safety population.

Overall, data for adverse events, clinical laboratory assessment, vital signs, ECG and other safety measurements (orthostatic hypotension, dyskinesia assessment, nasal inspection, \mp physical examination, subject questionnaire, domiciled status) will be presented by subject in listings (including assessments of abnormality and clinical significance, where applicable). Summaries will be prepared for key variables (detailed below) by cohort and treatment group and protocol specified time-point (where applicable) for the Safety population.

No inferential statistical testing will be performed for any safety variable.

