11.1. Adverse Events

Adverse events will be coded using MedDRA[®] Version 21.0. Adverse events will be grouped by system organ class (SOC) and preferred term (PT) and summarized, by actual treatment at time of onset of the AE. The summary tables will present the frequency and percentage of total subjects and number of events, by SOC and by PT.

For the summaries of AEs, subjects who experience the same AE (in terms of the MedDRA preferred term) more than once will only be counted once for that event in the number of subjects but all occurrences of the same event will be counted in the number of events.

AE summaries will include Treatment Emergent Adverse Events (TEAEs) and AE onset within benserazide period.

- TEAE is defined as AEs which commence on or after the time of first study drug administration (INP103 or placebo) through to the end of the study. AEs without an onset date or time will be defined as treatment emergent except if an incomplete date (e.g., month and year) clearly indicates that the event started prior to start of first study drug administration or if the AE stop date indicates that the event started and/or stopped prior to start of first study drug administration.
- AE onset within benserazide period: AE onset within the benserazide period is defined as the AE onset after the dose of benserazide and before the dose of INP103/ Placebo. AEs without an onset date or time will be defined into this category except if an incomplete date (e.g., month and year) clearly indicates that the event started prior to start of benserazide administration or if the AE stop date indicates that the event started and/or stopped prior to start of benserazide administration.

Incidence of adverse events as well as the duration, severity, relationship to treatment, outcome and actions taken will be listed for each subject. In addition, listings of AEs leading to discontinuation of the study, SAEs and deaths, will be provided if applicable.

‘Treatment Related’ TEAE is defined as any TEAE that is reported as having a *Definite, Probable* or *Possible* relationship to the study drug.

The following AE summaries will be provided:

- Overall summary of TEAEs, including below information
 - Any TEAE
 - AEs onset within Benserazide Period

CONFIDENTIAL AND PROPRIETARY

- Any severe TEAE
 - Any Treatment-related TEAE
 - Any serious TEAE
 - Any TEAE leading to study drug interruption
 - Any TEAE leading to study drug withdrawn

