| | 14.2.2.1 | Summary of Movement Disorder Society Unified Parkinson's Disease Rating Scale (MDS-UPDRS) Part III Score | ITT | Y | 1 |
| | 14.2.2.2 | MMRM of Movement Disorder Society Unified Parkinson's Disease Rating Scale (MDS-UPDRS) Part III Score | ITT | N | 2 |
| Figure | 14.2.2.3 | Individual Change from Baseline in Movement Disorder Society Unified Parkinson's Disease Rating Scale (MDS-UPDRS) Part III Score | ITT | N | 2 |
| | 14.2.2.4 | Summary of Cumulative Response | ITT | Y | 2 |
| | 14.2.2.5 | Summary of Time-to-Response | ITT | Y | 2 |
| | 14.2.2.6 | Duration of Response | ITT | N | 2 |
| Figure | 14.2.2.7 | Kaplan-Meier Plot for Time-to-Response | ITT | N | 2 |
| | 14.2.2.8 | Summary of AUC of change in Movement Disorder Society Unified Parkinson's Disease Rating Scale (MDS-UPDRS) Part III Score | ITT | N | 2 |

CONFIDENTIAL AND PROPRIETARY

| Header | Table Number | Table Title | Analysis Population | Interim Analysis | Priority |
|--------|--------------|--|---------------------|------------------|----------|
| | 14.2.2.9 | ANCOVA of AUC of change in Movement Disorder Society Unified Parkinson's Disease Rating Scale (MDS-UPDRS) Part III Score | ITT | N | 2 |
| | 14.2.2.10 | Summary of the Maximum Response | ITT | Y | 2 |
| | 14.2.2.11 | ANCOVA of The Maximum Response | ITT | N | 2 |
| | 14.2.2.12 | Summary of Time-to-ON | ITT | Y | 2 |
| Figure | 14.2.2.13 | Kaplan-Meier estimator for Time-to-ON status | ITT | N | 2 |
| | 14.2.3 | Pharmacokinetic versus Pharmacodynamic Relationship | | | |
| Figure | 14.2.3.1 | Time-matched Change from baseline in MDS-UPDRS Part III score versus uncorrected plasma L-Dopa concentrations | ITT | N | 2 |
| 14.3 | | Safety Data Summary Tables | | | |
| | 14.3.1 | Adverse Events | | | |
| | 14.3.1.1 | Overall Summary of Treatment Emergent Adverse Events | Safety | Y | 1 |
| | 14.3.1.2 | Adverse Events onset within Benserazide Period | Benserazide Safety | N | 2 |
| | 14.3.1.3 | Treatment Emergent Adverse Events | Safety | Y | 1 |
| | 14.3.1.4 | Treatment Emergent Adverse Events by Severity | Safety | N | 2 |
| | 14.3.1.5 | Treatment-Related Treatment Emergent Adverse Events | Safety | N | 2 |
| | 14.3.1.6 | Serious Treatment Emergent Adverse Events | Safety | N | 1 |
| | 14.3.2 | Listings of Deaths, Other Serious and Significant Adverse Events | Not Applicable | | |

CONFIDENTIAL AND PROPRIETARY

| Header | Table Number | Table Title | Analysis Population | Interim Analysis | Priority |

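### One row of the overall AE table sets benserazide-period AEs against the Safety Population, which makes its pooled-placebo and Overall percentages 25–33% too low in relative terms (minor)

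*SAP*

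**What the plan says.** SAP 11.1 names two kinds of AE for summary: TEAEs, and AEs that start after benserazide but before INP103 or placebo. Its list of contents for the overall TEAE summary includes the second kind as the row "AEs onset within Benserazide Period".

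The table list in SAP 17.2.2 gives the population for each table:

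- the overall summary: "14.3.1.1 | Overall Summary of Treatment Emergent Adverse Events | Safety | Y | 1"
- the stand-alone table of the same events: "14.3.1.2 | Adverse Events onset within Benserazide Period | Benserazide Safety | N | 2"

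Two general rules support the first assignment, and neither states an exception. SAP 6.5.4 says "All safety results will be generated on Safety Population", and SAP 11 says "All safety analyses will be conducted on the Safety population".

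SAP 6.5.3 says otherwise for these data. It creates the Benserazide Safety Population for safety data collected between benserazide and INP103 or placebo, and adds: "This population will not be applicable to Cohort 4". Protocol 12.2 defines the population in the same way.

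On denominators, SAP 8 sets percentages "with the denominator being the number of subjects in the relevant population, unless otherwise stated". SAP 7.1 pools placebo subjects from all cohorts into one group, and SAP 6.2 lays out the columns as placebo, the four dose cohorts and Overall.

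**The concern.** A benserazide-period AE can occur only in someone who took benserazide, which means Cohorts 1 to 3. The Safety Population is everyone who received any INP103 or placebo, so it also holds all dosed Cohort 4 subjects, including the 2 or 3 Cohort 4 placebo subjects in the pooled placebo column. They enlarge the denominator and cannot contribute an event.

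There is a smaller problem with the numerator. Benserazide is taken about an hour before dosing, and a subject judged to be ON at any time up to dosing is not dosed (SAP 4). Such a subject belongs to the Benserazide Safety Population but not to the Safety Population, so any event in that hour would be absent from the row.

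Two planned tables would therefore give different percentages for the same events. The row would also show placebo lower than the 35, 70 and 140 mg columns for a reason unrelated to treatment, since these events come before any INP103 or placebo is given.

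**Working it through.** **Inputs** (SAP 4.2 allocation table; the benserazide rule is in SAP 4):

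- Cohorts 1, 2 and 3: 6 active and 2 placebo each, all to receive benserazide. That is 18 active + 6 placebo = 24 subjects.
- Cohort 4: 6 to 9 active and 2 to 3 placebo, 8 to 12 subjects, none to receive benserazide.

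**The plan's own totals.** 4 × 8 = 32 and 3 × 8 + 12 = 36. These match the minimum of 32 and maximum of 36 in SAP 4.2.

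**Formula.** For a fixed number of affected subjects, the printed percentage divided by the percentage among exposed subjects equals (number given benserazide) / (Safety Population N in that column). Relative shortfall = 1 − that ratio.

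| Column | Given benserazide | Safety Population N | Ratio | Relative shortfall |
|---|---|---|---|---|
| Pooled placebo, Cohort 4 has 8 | 6 | 6 + 2 = 8 | 0.75 | 25.0% |
| Pooled placebo, Cohort 4 has 12 | 6 | 6 + 3 = 9 | 0.667 | 33.3% |
| Overall, Cohort 4 has 8 | 24 | 24 + 8 = 32 | 0.75 | 25.0% |
| Overall, Cohort 4 has 12 | 24 | 24 + 12 = 36 | 0.667 | 33.3% |
| INP103 35, 70 or 140 mg | 6 | 6 | 1 | 0% |

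For Cohort 4 sizes of 9, 10 and 11 the Overall shortfall is 27.3%, 29.4% and 31.4%.

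**Effect on printed figures.**

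- One affected placebo subject: 1/6 = 16.7% on the Benserazide Safety Population, against 1/8 = 12.5% or 1/9 = 11.1% on the Safety Population.
- Two affected placebo subjects: 2/6 = 33.3%, against 2/8 = 25.0% or 2/9 = 22.2%.
- With equal true rates, each benserazide-exposed INP103 column would appear 1/0.75 = 1.33 to 1/0.667 = 1.5 times placebo.

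**Interim run.** Table 14.3.1.1 is also produced at the interim, but SAP 5.1 limits that to Cohorts 1 and 2. All of those subjects are due to receive benserazide, so Cohort 4 does not enter the denominator.

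**The case against.** The best reply is that the row's denominator is inferred. SAP 8 refers to the relevant population, and SAP 6.5.3 says which population is relevant to these data. A specific rule normally overrides a general one, so a careful programmer might use the Benserazide Safety N for this row. That reading is possible, but it does not settle the matter. SAP 17.2.2 labels the whole table Safety, SAP 6.5.4 and 11 say the same of all safety output, and no row-level exception is written. The labels as they stand lead to the Safety N.

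Column attribution is also not fully settled. SAP 11.1 summarizes AEs by the treatment actually being received at onset, and at that time only benserazide has been given. SAP 11 speaks of summaries by cohort and treatment group. If placebo were split by cohort, the placebo distortion would disappear, but the Overall one would remain. SAP 6.2 and 7.1 specify pooled placebo.

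Several limits on importance stand in full. The events are already reported properly in Table 14.3.1.2, and the AE listing runs on the ITT Population, which SAP 6.5.2 defines as all randomized subjects, dosed or not. SAP 6.1 drops a row that is zero throughout, so with no such event it would not appear. Counts are printed beside percentages (SAP 6.4), and SAP 11 rules out inferential testing of safety variables.

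A reader might infer three stronger things that the documents do not support:

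- *That the primary safety result is distorted.* The primary endpoint (SAP 3.2.1) covers the 240 minutes after dosing and the 7-day follow-up. Benserazide-period AEs come before dosing and are not TEAEs. The TEAE rows of Table 14.3.1.1 belong on the Safety Population.
- *That events are lost from the report.* At most they are absent from one duplicate summary row.
- *That the Cohort 4 column will print 0% as if observed.* SAP 6.4 refers to table shells, but the text available holds only the list of tables, so how that cell will print cannot be checked.

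**Conclusion.** The inconsistency is real and minor. SAP 6.5.3 assigns benserazide-period AEs to one population, while SAP 11.1 with 17.2.2 places them in a table run on another. In the final analysis, followed as labelled, the row's pooled-placebo and Overall percentages would be 25.0% to 33.3% too low as estimates of the rate among exposed subjects. These are relative shortfalls, not percentage points. The same events would carry different percentages in Table 14.3.1.2.

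The figures assume planned enrolment, all randomized subjects dosed, pooled placebo, and the Safety N applied to every row of Table 14.3.1.1. Subjects given benserazide but not dosed would add a further undercount, and the documents give no number for them.

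The consequence is confined to one descriptive row of pre-dose events.

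**What to change.** In SAP 11.1, do one of the following:

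- remove the benserazide-period row from Table 14.3.1.1 and rely on Table 14.3.1.2; or
- keep the row with the Benserazide Safety Population N as its denominator (planned: 6 placebo and 24 Overall, plus anyone given benserazide but not dosed), show NA for Cohort 4, and footnote the change of population.

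In SAP 6.5.4 and 11, except benserazide-period AEs from the rule that all safety output uses the Safety Population.

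The cost is a few lines of SAP text and one table shell. No new data are needed and trial conduct does not change.

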11.2. Serious Adverse Events

Incidence of SAEs as well as the duration, severity, relationship to treatment, outcome and actions taken will be listed for each subject.

11.3. Adverse Events Leading to Dose Interruption, Discontinuation of Investigational Product and/or Withdrawal from the Study and Other Significant Adverse Events

Incidence of AE's leading to study dose interruption, withdrawal or discontinuation from study, as well as the duration, severity, relationship to treatment, outcome and actions taken will be listed for each subject.

11.4. Clinical Laboratory Evaluations

All individual clinical laboratory results (hematology, biochemistry and urinalysis) will be presented in data listings. Values outside the laboratory reference range will be flagged (low-L, high-H).

When applicable, observed and change from baseline (prior to the first study drug administration [benserazide or INP103/placebo]) clinical laboratory data (hematology and biochemistry) will be summarized by cohort and treatment group and protocol specified collection time point. Urinalysis results will be summarized using frequency tabulation. Frequency tabulations of the number of normal and abnormal (low and high) records, as well as the number of clinically significant (CS) and not clinically significant (NCS) for clinical laboratory results (hematology, biochemistry and urinalysis) will also be summarized by cohort, treatment group and protocol specified collection time point.

CONFIDENTIAL AND PROPRIETARY

Any available microscopic urinalysis will be listed only.

11.5. Vital Signs Evaluations

All individual vital signs results (supine and standing systolic blood pressure [mmHg], supine and standing diastolic blood pressure [mmHg], heart rate [beats per minute (bpm)], respiratory rate [breaths per minute] and oral temperature [°C]) will be presented in data listings. Observed vital signs parameter values and changes from baseline (prior to the first study drug administration [benserazide or INP103/placebo]) will be summarized by treatment and protocol specified collection time point.

11.6. ECG Evaluations

All individual ECG parameter values (Heart Rate [bpm], QT interval [msecs], PR interval [msecs], QRS interval [msec], RR interval [msecs], QTcF [msecs], and QTcB [msecs]) and overall ECG clinical interpretation will be presented in data listing. Observed ECG parameter values and changes from baseline (prior to the first study drug administration [benserazide or INP103/placebo]) will be summarized by treatment and protocol specified collection time point.

In addition, clinical assessment of the ECG (Normal, Abnormal NCS, and Abnormal CS) will be summarized by cohort and treatment group and protocol specified collection time point, using frequency tabulations.

Furthermore, the proportion of subjects meeting the following criteria based on QTc values (defined both using the correction by Bazett and by Fridericia) will be summarized by treatment group, using frequency tabulations:

- QTc value >500 msec
- QTc value increasing >15% from baseline if baseline value is ≥ 440 msec
- QTc value increasing >30% from baseline if baseline value is <440 msec
- QTc value increasing >30% from baseline
- QTc value increasing >60% from baseline

11.7. Other Safety Measures

11.7.1. Dyskinesia Examination

The result of dyskinesia examination will be presented in data listing. The Dyskinesia Grade (Grade 0 to 4) will be summarized by cohort and treatment group and protocol specified collection time point, using frequency tabulations.

11.7.2. Nasal Examination

The result of nasal examination will be presented in data listing. All nasal examination categories (Inflammation, Ulceration, Contact bleeding, Oedema, and Other) will be summarized by cohort and treatment group and protocol specified collection time point, using frequency tabulations.

11.7.3. Orthostatic hypotension

The proportion of subjects experiencing orthostatic hypotension will be summarized by cohort and treatment group and protocol specified collection time point, using frequency tabulations, if applicable.

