7.4.3. After Dosing

The subjects will remain in the study clinic post-dose through to the completion of all scheduled post-dose procedures 240 minutes after dosing.

The subject's usual rescue (anti-OFF [e.g. Madopar rapid]) medication will be permitted from 120 minutes post-dose (once all 120 minute assessments have been completed, but can precede ECG, physical examination and subject questionnaire) – if they are still OFF. In addition, subjects should take their regular anti PD medication (e.g. their regular morning Madopar dose) at 120 minutes post dosing whether or not they have returned to ON.

The following in-patient assessments will be performed after dosing:

1. Adverse Events (including overall dyskinesia rating) and concomitant medications will be continually monitored post-dose.
2. Vital signs will be measured at 30, 60 and 120 minutes post-dose. Blood pressure (supine and standing) and heart rate, respiratory rate and oral temperature (supine only) will be measured at all time points. Vital signs will be collected after MDS-UPDRS assessment (where both procedures are scheduled at the same time point) and will not be deemed protocol deviations if they occur outside the time window at each timepoint.
3. PK blood samples will be collected at 4, 9, 14, 29, (all + 1 minute) 44, 59, 89 and 119 (all \pm 2 minutes at each timepoint) minutes post-dose and will precede UPDRS assessments.
4. MDS-UPDRS III only at 15, 30, 45, 60, 90 and 120 minutes post-dose for Cohorts 1, 2 and 3) and 30, 60, 90, 120 minutes for Cohort 4 (\pm 2 minutes at each timepoint)
5. Investigator and subject self-assessment of ON/OFF at 30, 45, 60, 90, 120 and 240 minutes post-dose (\pm 10 minutes at each timepoint)
6. At 120 minutes, the subject's usual morning dose of all Parkinson's medications should be given following completion of assessments 1-5, regardless of ON/OFF state. In addition, if subject is still OFF, their usual OFF medication may be given (prior to completing assessments 7, 8 and 9).
7. Directed physical examination (including nasal inspection) will be performed at 120-180 minutes post-dose

8. 12-Lead ECG will be performed at 120-180 minutes post dose. In cases where vital signs are scheduled at the same time point, ECG will be completed in sequence with vital signs per the usual practice of the study sites.
9. Subject questionnaire will be completed as the last assessment from 120-180 minutes post-dose

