7.5. Follow-Up/End of Study (Day 7 + 2 days)

The subjects will return to the institution on Day 7 (+2 days). In exceptional circumstances, if a subject is unable to attend the end of study visit on Day 7 (+ 2 days, as indicated), the Investigator (or qualified designee) should discuss appropriate re-scheduling to a maximum of +4 days with the Sponsor's Medical Monitor (or appropriate designee). The following assessments will again be carried out:

- Adverse Events (including overall dyskinesia rating) and concomitant medications
- 12-Lead ECG
- Vital signs (blood pressure [supine and standing]; and heart rate, respiratory rate and oral temperature [supine only])
- Complete physical examination
- Clinical laboratory testing (haematology, serum chemistry and urinalysis)
- Full MDS-UPDRS

Due to variability in assessment length, assessments collected out of window, with the exception of PK samples and UPDRS, will not be considered deviations

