Subjects will be enrolled into one of four dose treatment cohorts with at least 8 subjects per cohort. All subjects in Cohorts 1, 2, 3 will receive oral DCI, benserazide hydrochloride, 25 mg at 60 ± 5 minutes before dosing with INP103 or placebo. Subjects in Cohort 4 will receive the DCI as carbidopa at 1/10th the dose of, and with, L-dopa via the POD device. At the discretion of the Sponsor, depending on rate of recruitment, cohort 4 may be over enrolled with a total of up to 12 subjects using the 3:1 randomization scheme.

On Day 0 (Visit 3), subjects in each cohort will be randomized to receive treatments as follows:

| Cohort | Treatment (Study Drug) |
|--------|---|
| 1 | INP103 35 mg L-dopa (n=6); Placebo (n=2) |
| 2 | INP103 70 mg L-dopa (n=6); Placebo (n=2) |
| 3 | INP103 140 mg L-dopa (n=6); Placebo (n=2) |
| 4 | INP103 70 mg L-dopa/7.0 mg carbidopa (n=6, maximum 9); Placebo (n=2, maximum 3) |

Cohorts will be enrolled and dosed in sequence. Escalation to the next higher dose cohort (Cohorts 1 to 2 and 2 to 3) may only commence after review and approval of safety data by a Safety Monitoring Committee (SMC). Interim analysis of data will be conducted upon completion of Cohort 1 and 2 study procedures, at the discretion of the Sponsor, depending on rate of recruitment. In this scenario, Cohort 1 and 2 data will be soft-locked, patients may be unblinded and tables, listings, and figures of collected data will be produced. Unblinding of Cohort 1 and 2 data will not jeopardize blinding of any enrolled Cohort 3 or 4 subjects at the time of the interim analysis.

Interim Analysis

An interim analysis (IA) will be completed after Cohorts 1 and 2. Cohorts 1 and 2 data will be soft-locked and a subset of tables and listing will be provided. Subject level treatment allocations will not be provided to the sponsor. The aim of this analysis is to generate preliminary safety, efficacy and PK information from Cohorts 1 and 2 only.

To maintain the overall blinding of this study in the first instance, the IA tables and listings will be provided in the following way:

- For the specified demographic/baseline, adverse event and other safety listings, treatment will not be included/printed in the presentation. Data for the specified demographics/baseline and adverse events will be summarized by Cohort only, with data from active subjects and placebo subjects pooled for each cohort.

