Continuous safety data will be summarized with descriptive statistics (arithmetic mean, SD, median, minimum, and maximum) by treatment. Categorical safety data will be summarized with frequency counts and percentages by treatment.

AEs will be coded using the Medical Dictionary for Regulatory Activities (MedDRA®) version 21.0. A by-subject AE data listing, including verbatim term, preferred term, system organ class, treatment, severity, and relationship to INP103 or placebo, will be provided. The number of subjects experiencing treatment emergent AEs (TEAEs) and number of individual TEAEs will be summarized by treatment, system organ class and preferred term. TEAEs will also be summarized by seriousness, severity, relationship to INP103 or placebo and the time of onset relative to dosing.

Dyskinesia assessment, nasal inspection, laboratory evaluations, vital signs assessments (including supine and standing blood pressure, all other vital signs supine only) and ECG parameters will be summarized by treatment and collection time point. A summary of change-from-baseline at each time-

point by treatment will be presented. In addition, the proportion of subjects experiencing orthostatic hypotension or abnormal ECGs will be summarized by treatment group.

Proportion of subjects with abnormal physical examination findings will be summarized by treatment group.

Prior and concomitant medications will be listed by subject and coded using World Health Organization (WHO) drug dictionary, Version MAR-2018 and summarized by therapeutic class (Level 4 for anti-PD medications and Level 2 for other medications) and preferred name.

Medical history will be listed by subject.

Pharmacokinetics:

Reported (i.e. uncorrected) and baseline corrected L-dopa concentrations will be summarized with descriptive statistics (arithmetic and geometric mean, SD, CV% median, minimum, and maximum) by treatment group and time point. In addition, PK parameters ($AUC_{0-0.5h}$, AUC_{0-1h} , AUC_{0-2h} , C_{max} , T_{max}) derived from both reported and baseline corrected L-dopa concentration data will be summarized with descriptive statistics by treatment group.

Exploratory Analysis

- PK profile of carbidopa (Cohort 4 only) for the first 120 minutes following dosing with INP103 will be summarized with the PK parameters of AUC_{0-2h} , C_{max} and T_{max} .

Pharmacodynamics:

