6.7.6. Other Derivations

Body Mass Index (kg/m^2 , to one decimal place) = Body Weight (kg) / (Height^2 (m)).

For any observed original results above the upper limit or below the lower limit in laboratory assessment, the original results will be presented in data listing and the upper limit value or the lower limit value will be used for summary table. For example, *0.1* will be used if the original result is “<0.1”, while *1000* will be used if the original result is “>=1000”.

Treatment emergent adverse events will be defined as AEs which commence on or after the time of start of first study drug administration. AEs without an onset date or time will be defined as treatment emergent except if an incomplete date (e.g., month and year) clearly indicates that the event started prior to start of first study drug administration or if the AE stop date indicates that the event started and/or stopped prior to start of first study drug administration.

Adverse event time since study drug administration (in minutes) = (Onset Date + Onset Time) – (Study Drug Administration Date + Study Drug Administration Time).

Duration of AE (in minutes) = (Resolution Date + Resolution Time) - (Onset Date + Onset Time).

The response is defined as an improvement of $\geq 30\%$ in MDS-UPDRS Part III score from baseline to post INP103/Placebo dosing time point for each patient.

Time to response = (Time at FIRST response [as defined above] post study drug administration [INP103/Placebo] – Time at the first study drug administration [INP103/Placebo] [Unit = minutes]).

The orthostatic hypotension is defined as a reduction in systolic blood pressure of 20 mmHg or more, and/or a reduction in diastolic blood pressure of 10 mmHg or more, for the standing measurement compared to the supine measurement.

All AUC values will be calculated by using the trapezoidal rule.

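### SAP 11.7.3 tabulates orthostatic hypotension only by collection time and names no by-subject row, although Protocol 12.3 and the SAP synopsis call for the share of subjects affected in each treatment group

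*SAP*

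**What the plan says.** The safety paragraph of the SAP synopsis has two steps. It lists vital signs, ECG and other measures as summarized by treatment and collection time. It then continues: "In addition, the proportion of subjects experiencing orthostatic hypotension or abnormal ECGs will be summarized by treatment group". No time point is attached to that sentence. Protocol 12.3 and the protocol synopsis are built the same way.

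SAP 11.7.3 specifies something different: "The proportion of subjects experiencing orthostatic hypotension will be summarized by cohort and treatment group and protocol specified collection time point". It names no row that counts a subject once across times.

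Other provisions that bear on the point:

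- **Definition.** SAP 6.7.6 begins "The orthostatic hypotension is defined as a reduction in systolic blood pressure of 20 mmHg or more" and goes on to the diastolic criterion. It compares one standing reading with one supine reading and has no rule for combining times.
- **Schedule.** Protocol 7.4.3: "Vital signs will be measured at 30, 60 and 120 minutes post-dose". Protocol 7.5 adds supine and standing blood pressure at Day 7.
- **Outputs.** Table 14.3.5.2 is the planned summary and Listing 16.4.1.2 the planned listing. Only their titles appear in the supplied text.
- **Precedence.** Protocol 12 lets the SAP override the protocol where they differ. SAP 6.5.2 states openly that its ITT definition departs from the protocol; 11.7.3 carries no such statement.

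**The concern.** The protocol and SAP synopsis set orthostatic hypotension apart from the measures tabulated by time, which reads most naturally as one proportion of subjects per group. The governing section then specifies only the by-time form. The SAP keeps the by-subject form elsewhere: the QTc criteria in 11.6, which come from the same paragraph of Protocol 12.3, remain proportions of subjects by treatment group.

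No other specified summary fully covers the gap. Under Protocol 8.4, abnormal vital signs are not adverse events in themselves; they become so only when clinically significant or accompanied by signs or symptoms. A drop that meets the numerical definition without either need not reach the adverse event tables, which do count each subject once per preferred term.

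Standing and supine blood pressure belong to the primary safety endpoint, and the primary objective is a comparison with placebo. A reader who takes the largest time-point row as the share of subjects affected may get too small a figure, and the gap need not be equal in the active and placebo groups.

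**Working it through.** The plan states no rate, count or sample size for orthostatic hypotension, so there is no figure to reproduce. The size can only be bounded.

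**Inputs from the documents**

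- Scheduled post-dose Visit 3 readings: k = 3 (30, 60, 120 minutes; Protocol 7.4.3).
- Active group size: 6, and 6 to 9 in Cohort 4 (SAP 4.2).
- Pooled placebo: 2+2+2+2 = 8, or 2+2+2+3 = 9 (SAP 4.2 and 7.1).

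**Assumed, because the documents are silent:** the proportion p at each time (5% to 30%), and the overlap between times (complete to none).

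**Bounds.** Let A be the proportion of subjects affected at one or more of k times, with proportion p at each time.

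- Lower limit, same subjects every time: A = p.
- Upper limit, different subjects every time: A = min(1, k × p).
- For reference, if times were independent: A = 1 − (1 − p)^k.

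**One affected subject at each of the three times**

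| Group | Each row shows | A, same subject | A, three different subjects |
|---|---|---|---|
| n = 6 | 1/6 = 16.7% | 1/6 = 16.7% | 3/6 = 50.0% |
| n = 8 (pooled placebo) | 1/8 = 12.5% | 1/8 = 12.5% | 3/8 = 37.5% |
| n = 9 | 1/9 = 11.1% | 1/9 = 11.1% | 3/9 = 33.3% |

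**By assumed rate, k = 3**

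| p at each time | Lower limit | Independence | Upper limit |
|---|---|---|---|
| 5% | 5% | 1 − 0.95³ = 14.3% | 15% |
| 10% | 10% | 1 − 0.90³ = 27.1% | 30% |
| 20% | 20% | 1 − 0.80³ = 48.8% | 60% |
| 30% | 30% | 1 − 0.70³ = 65.7% | 90% |

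**Effect on a comparison.** Suppose every row shows 1/6 on active and 1/8 on placebo. Each row then differs by 16.7 − 12.5 = 4.2 percentage points. The by-subject difference could lie anywhere from 1/6 − 3/8 = −20.8 points to 3/6 − 1/8 = +37.5 points. The specified rows cannot tell these cases apart.

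**The case against.** **The by-subject reading is inferred.** Neither the protocol nor the SAP synopsis says at any time or gives a window, and 11.7.3 could be read as adding detail to a sentence that left timing open. SAP 11.7.4 likewise adds time points to the physical examination summary. This stands as a caution about intent. It does not supply the missing quantity, and the two-step structure of the paragraph together with the QTc treatment favours the by-subject reading.

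**A reader might infer that affected subjects are never added up.** The documents do not support that. Listing 16.4.1.2 allows a hand count, which is easy in groups of 6 to 9. SAP 6.4 also treats the table shells as part of the SAP, and the rows of Table 14.3.5.2 are not in the supplied text. What can be said is that 11.7.3 names no such row.

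**A reader might infer that the incidence is understated.** That is conditional. It requires a time-point row to be taken for the overall share, and different subjects to be affected at different times. Nothing in the documents supports independence of repeated readings in one person, so the independence column is illustrative only.

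**Clinically important cases are already counted.** Significant or symptomatic drops that meet the adverse event definition enter the by-subject event tables. SAP 11 plans no inferential testing of safety variables, so no formal test depends on this row. Both points limit the consequence.

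**A careless any-time row could mislead.** It could count subjects who met the definition before dosing. It could also mix in readings taken after usual medication: Protocol 7.4.3 places vital signs before that medication at 120 minutes, but a Table 1 footnote lets the 120-minute vital signs run to 180 minutes. This objection is sound, and the added row has to deal with it.

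**Abnormal ECGs.** The same protocol sentence names them, so a reader might want a matching ECG row. Only one post-dose ECG is scheduled at Visit 3, so an any-time row there would repeat the existing one.

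**Conclusion.** SAP 11.7.3 differs from Protocol 12.3 and from the SAP's own synopsis, and the summary it specifies omits the share of subjects affected after dosing. The rows it does specify are correct for their own times. Over the three Visit 3 readings the by-subject share lies between one and three times the largest row; for n=6 with 1/6 in every row, that is 16.7% to 50.0%. The actual gap is unknown and may be zero. The bounds need only the schedule and group sizes; the percentage rates in the second table are assumptions. This is a modest, inexpensive gap in the reporting of part of the primary safety endpoint. It does not show that incidence will be under-reported.

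**What to change.** Add to SAP 11.7.3 and Table 14.3.5.2 one row for each dose group and for pooled placebo: subjects with orthostatic hypotension at one or more scheduled post-dose Visit 3 assessments (30, 60, 120 minutes). With it:

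- keep the time-point rows as support;
- show Day 7 separately, since usual Parkinson's medication has resumed by then;
- show separately the subjects who already met the definition before dosing, so that pre-existing cases are not read as post-dose events;
- flag nominal 120-minute readings taken after usual Parkinson's medication resumed.

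Restricting the row to scheduled assessments keeps it clear of a difference within the SAP: 6.4 and 8.5.3 allow extra measurements in tables that are not time-specific, while section 8 keeps data from unscheduled visits out of summary tables.

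The cost is one extra table row with its accompanying split and flag. No new data are needed, and no change to the ECG tables is proposed.
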